12.4 Clinical Efficacy

Clinical efficacy evaluation will include tumor response assessed by irRECIST, Progression-free Survival and overall survival.

The primary endpoint will test the 3-month progression free survival rate in the platinum resistant group in conjunction with the 6-month progression free survival rate in the platinum sensitive group. The overall test follows the approach of London and Chang(58) Let π_1 denote the 3 month progression free response rate for the platinum-resistant strata and let π_2 denote the 6 month progression free response rate for the platinum sensitive strata. Our overall test is of the form $H_0: \pi_1 = 0.55, \pi_2 = 0.65$ versus the alternative $H_1: \pi_1 > 0.55, \pi_2 > 0.65$. Using the approach of

London and Chang our test statistic takes the form $T = \frac{R - \sum_i^2 N_i \pi_{i0}}{\sqrt{N \sum_{i=1}^2 \pi_{i0} (1 - \pi_{i0}) P_i}}$, where R denotes the combined number of non-progressors across strata, $\pi_{10} = 0.55$ and $\pi_{20} = 0.65$ represent the null values for strata 1 and 2 above, $N = N_1 + N_2$ $N_1 = 18$ and $N_2 = 9$ represent the strata sample sizes and $P_1 = 2/3$ and $P_2 = 1/3$ represent the strata distribution proportions, respectively. The distributional properties of T are given in London and Chang (58). Given $\alpha = 0.10$ and a fixed sample size of $N = 27$ we will be able to detect a difference of 0.2 and 0.15 between the null and alternative progression free survival rate values per strata one and two, respectively at 0.72 power based on an exact multinomial test about T .

All patients who received at least two cycles of durvalumab + tremelimumab and 8 weeks of olaparib, as well as baseline and at least one post-baseline disease assessment will be evaluated for clinical efficacy. Tumor Responses by irRECIST and RECIST, progression free survival and overall survival will be summarized and analyzed descriptively via summary frequencies and Kaplan-Meier estimators.

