4.3 Replacement of Participants

Patients who are not considered fully evaluable per protocol for the primary objective of safety and tolerability may be replaced. The period for evaluating DLTs will be from the time of first administration of durvalumab, tremelimumab, and olaparib until at least two cycles of durvalumab (8 weeks). Subjects who do not remain on the study up to this time for reasons other than DLT will be replaced with another subject at the same dose level. The compliance requirement for olaparib is 75% of the planned dose during the first 8 weeks. This applies to both Phase I and Phase II part of the study. There will be no replacement of patients during retreatment.

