6.8 Treatment Discontinuation

Upon treatment discontinuation all end of treatment evaluations and tests will be conducted. All participants who discontinue due to an AE must be followed until the event resolves or stabilizes. Appropriate medical care should be provided until signs and symptoms have abated, stabilized, or until abnormal laboratory findings have returned to acceptable or pre-study limits. The final status of the AE will be reported in the participant’s medical records and the appropriate eCRF.

An individual subject will not receive any further investigational product if any of the following occur in the subject in question:

1. Withdrawal of consent or lost to follow-up.
 - a. If consent is withdrawn, the subject will not receive any further investigational product or further study observation.
2. Adverse event that, in the opinion of the investigator or the sponsor, contraindicates further dosing
3. Subject is determined to have met one or more of the exclusion criteria for study participation at study entry and continuing investigational therapy might constitute a safety risk.
4. Pregnancy or intent to become pregnant.

5. Any AE that meets criteria for discontinuation as defined in Section 10.1.
6. Adverse Event or DLT that, in the opinion of the Investigator, contraindicates further dosing (See Section 6.4 for definition of DLT).
7. Grade ≥ 3 infusion reaction.
8. Subject noncompliance that, in the opinion of the investigator or sponsor, warrants withdrawal; e.g., refusal to adhere to scheduled visits.
9. Initiation of alternative anticancer therapy including another investigational agent.
10. Confirmation of PD and investigator determination that the subject is no longer benefiting from treatment.
11. Development of intercurrent, non-cancer related illnesses that prevent either continuation of therapy or regular follow up.

Subjects who are permanently discontinued from further receipt of investigational product, regardless of the reason (withdrawal of consent, due to an AE, other), will be identified as having permanently discontinued treatment.

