17. CT (preferred) or MRI scans, preferably with IV contrast, are collected during screening (for baseline), as close to and prior to initiation of study treatment. Timing of on-treatment CT/MRI scans is pre-dose C4D1 (± 7 days) for biopsy site determination and every 3 cycles thereafter (i.e. Day 1 of Cycles 7, 10, 13 ± 7 days) or as clinically indicated until progressive disease or off-study. Response according to irRECIST criteria (irCR, irPR) requires a confirmatory scan preferably at the next regularly scheduled imaging visit and no earlier than 6 weeks after the prior assessment of CR, PR, or SD is deemed by irRECIST. End of Treatment disease assessment does not need to be repeated if performed within 28 days prior to end of treatment.
18. Refer to Table 7 for details.
19. Refer to Appendix H and Appendix I for follow-up visits.
20. Results from CA-125 and thyroid function test do not need to be available prior to dosing patient on dosing days.

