12.3 Safety and Tolerability

The primary objective of the Phase I study is establishing safety. Assessment of safety and tolerability will be performed by the internal data safety monitoring panel on an ongoing basis, based on data review and regular conference calls with the investigators.

DLT: All patients who receive at least two cycles of durvalumab + tremelimumab and 8 weeks of olaparib treatment and respective safety assessments, as well as, all patients who discontinue the study prematurely due to DLT are considered fully evaluable per protocol for DLT (see Section 4.3 for patient replacement). Patients must also have received at least 75% of the planned dose of olaparib during the DLT evaluation period (except for patients who discontinued prematurely due to DLT) to be evaluable for DLT.

Safety set: All patients who received at least one dose of durvalumab + tremelimumab + olaparib will be evaluated for safety and tolerability.

Appropriate summaries of AEs, laboratory data and vital sign data will be presented. AEs will be listed individually per patient according to CTCAE version 4.03, and the number of patients experiencing each AE will be summarized using descriptive statistics.

The MTD is defined as the highest dose studied, for which the observed incidence of DLT is less than 33%. Frequencies of toxicities will be tabulated according to the National Cancer Institute Common Terminology Criteria for Adverse Events (CTCAE) version 4.03.

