Survival status: phone contact with subjects who refuse to return for evaluations and agree to be contacted		X	X	X	X	X	X	X (every 2 months)
Hematology ^c	X	X	X					
Chemistry ^d	X	X	X					
Thyroid function tests (TSH, and fT3 and fT4) ^e	X							

Evaluation	Time Since Last Dose of Durvalumab or Tremelimumab or Olaparib							
	Day (± 3)	Months (± 1 week)						12 Months and Every 6 Months (± 2 weeks)
	30	2	3	4	6	8	10	
Tumour assessment (CT or MRI)	
For subjects who achieve disease control following 12 months of treatment, tumour assessments should be performed every 12 weeks relative to the date of first infusion thereafter until confirmed PD by irRECIST by investigational site review. Please refer to Table 5 for timings of confirmatory scans.
 
For subjects who discontinue durvalumab + tremelimumab due to toxicity (or symptomatic deterioration), tumour assessments should be performed relative to the date of first infusion as follows: every 12 weeks until confirmed PD by irRECIST by investigational site review or started on standard therapy or another clinical study. Please refer to Table 5 for timings of confirmatory scans.
 
Upon confirmed PD or initiation of standard therapy, scans should be conducted according to local standard clinical practice.
							

- a Full physical exam (refer to Section 8.3.2).
- b Refer to Section 8.3.4.
- c Refer to Section 8.3.5, Table 6..
- d Refer to Section 8.3.5, Table 7.
- c Free T3 and free T4 will only be measured if TSH is abnormal. They should also be measured if there is clinical suspicion of an adverse event related to the endocrine system.

Appendix I Schedule of study procedures: follow-up for subjects who have discontinued study treatment due to confirmed progression of disease at the investigator discretion

Evaluation	Time Since Last Dose of Durvalumab or Tremelimumab or Olaparib						
	Day (± 3)	Months (± 1 week)					
	30	2	3	4	6	8	10
Physical examination ^a	X						
Vital signs (temperature, respiratory rate, blood pressure, pulse) ^b	X						
Weight	X						
AE/SAE assessment	X	X	X				
Concomitant medications	X						
Palliative radiotherapy	As clinically indicated						
ECOG performance status ^c	X					→	
Subsequent anti-cancer therapy	X	X	X	X	X	X	X
Survival status: phone contact with subjects who refuse to return for evaluations and agree to be contacted		X	X	X	X	X	X (every 2 months)
Hematology ^d	X						
Chemistry ^e	X						
Thyroid function tests (TSH, and fT3 and fT4) ^f	X						

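### Section 12.4's only efficacy population selects on early outcome, and no sentence says whether it or all 27 Phase II patients supply R in the primary PFS test

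*Combined protocol and SAP*

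**What the plan says.** Section 12.4 names progression-free survival among the clinical efficacy evaluations and then sets out a stratified one-sided test. It uses 3-month PFS in the platinum-resistant stratum (null 0.55) and 6-month PFS in the platinum-sensitive stratum (null 0.65). The statistic is built on R, "where R denotes the combined number of non-progressors across strata", with N1=18, N2=9, a fixed N of 27, alpha 0.10 and stated power 0.72. No analysis set is attached to R.

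After the test, the same section restricts efficacy evaluation to patients with "at least two cycles of durvalumab + tremelimumab and 8 weeks of olaparib, as well as baseline and at least one post-baseline disease assessment". No other efficacy set appears. The safety set in Section 12.3 (at least one dose) is for safety and tolerability only.

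Other passages that bear on this:
- The DLT set in Section 12.3 has the same two-cycle, 8-week rule but adds back the event of interest: "all patients who discontinue the study prematurely due to DLT are considered fully evaluable per protocol for DLT".
- Section 4.3: "Subjects who do not remain on the study up to this time for reasons other than DLT will be replaced". Two sentences later, directly after the olaparib compliance requirement, it says that this covers both phases.
- Table 5, footnote 17: "Timing of on-treatment CT/MRI scans is pre-dose C4D1", which is about week 12.
- Section 6.8: "Upon treatment discontinuation all end of treatment evaluations and tests will be conducted". Table 5 includes a disease assessment at that visit.
- Appendix H continues scans after a toxicity stop, "every 12 weeks until confirmed PD by irRECIST by investigational site review or started on standard therapy or another clinical study".

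**The concern.** Membership of the Section 12.4 set depends on what happens after treatment starts, and unlike the DLT set it has no clause bringing back patients who leave because of the event being measured. If it supplies R:

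- **Dropped although they are PFS failures:** patients who die or stop with progression before 8 weeks, and patients who die later, before any post-baseline scan. This raises the observed rates.
- **Dropped while progression-free:** patients who stop for toxicity before 8 weeks. Appendix H would often show their landmark status, but it would go unused. This lowers the observed rates.
- **Dropped with status unknown:** patients who leave after 8 weeks with no post-baseline scan.
- **Kept:** progressors who go on dosing to 8 weeks and are scanned, including most of those found at the week-12 scan, and patients who leave in weeks 8 to 12 and have the end-of-treatment scan.

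The test compares R with fixed null rates and has no control arm to absorb a selection effect. With 27 patients, the treatment of one patient can decide the result.

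**Working it through.** **Inputs from Section 12.4.** N1=18, N2=9; nulls 0.55 and 0.65; alternatives 0.55+0.20=0.75 and 0.65+0.15=0.80; one-sided alpha 0.10. The excluded share f, and the share q of excluded patients who are progression-free at the landmark, are not in the documents. They are assumed below and taken as equal in both strata.

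**Step 1: reproduce the plan's figure.** R is Bin(18, p1) + Bin(9, p2), convolved exactly. Under the null the mean is 18×0.55 + 9×0.65 = 15.75. The variance is 27×(0.2475×2/3 + 0.2275×1/3) = 6.5025, so the SD is 2.55.

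- Null: P(R>=19)=0.140, P(R>=20)=0.068. The cutoff implied by alpha 0.10 is R>=20, where T=(20−15.75)/2.55=1.667.
- Alternative: P(R>=20)=0.717, which matches the stated 0.72.

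These properties hold if R and N cover everyone to whom 0.55 and 0.65 apply.

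**Step 2: N=27 and R>=20 kept, no replacement.** An excluded patient cannot add to R, so each rate becomes (rate − f×q).

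- q=0 (all failures): size 0.068 at any f.
- q=0.5: size 0.040, 0.022, 0.012 and power 0.60, 0.49, 0.37 at f=5%, 10%, 15%.

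There is no inflation. The cost is power.

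**Step 3: N cut to the evaluable number.** Suppose R=19 of 27 (p=0.140, not significant). Removing one early failure leaves R=19 of 26. The exact p is 0.091 if she was platinum-resistant (17+9) and 0.085 if platinum-sensitive (18+8). Both are below 0.10.

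That example fixes exactly one removed failure. Averaged over a binomial number of exclusions, with the cutoff recomputed each time, size at f=3.7% (one in 27 expected) is 0.111 if all are failures and 0.093 if three quarters are.

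**Step 4: excluded patients replaced, N=27, R>=20.** Remaining rate = (null − f×q)/(1−f). For example, f=5% and q=0 gives 0.55/0.95=0.579 and 0.65/0.95=0.684.

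| f | all failures (q=0) | half and half (q=0.5) | all progression-free (q=1) |
|---|---|---|---|
| 5% | 0.121 | 0.074 | 0.043 |
| 10% | 0.211 | 0.082 | 0.024 |
| 15% | 0.351 | 0.090 | 0.012 |

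At f=3.7% with q=0 the size is 0.105. The excluded share at which 0.10 is passed is 3.3% if all are failures, 5.6% if three quarters are, and 19.5% if half are.

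**The case against.** The other side has real strength.

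- **N is stated.** Section 12.4 fixes N at 27 with 18 and 9 in the strata, equal to planned Phase II enrolment. A reader might infer that the plan leaves N open; it does not. Cutting N would depart from the written statistic, and if 27 is kept without replacement there is no inflation. This stands. But no sentence says that all enrolled patients supply R, and the evaluable-set sentence points the other way.
- **The evaluable set may serve only the descriptive summaries.** The sentence follows the complete test specification, and the next one describes frequencies and Kaplan-Meier estimates. That is a possible reading. It is unstated, and PFS is listed under the clinical efficacy that the set governs.
- **Replacement may not reach Phase II.** Section 4.3 opens with evaluability for safety and ties replacement to the DLT period and dose level. Section 6.4 places DLT evaluation in Phase I. The sentence covering both phases may refer only to olaparib compliance. The cap of 36 in Section 4.2 leaves no spare place if Phase I used nine (9+27). Replacement is therefore one reading, not an established rule.
- **Few progressors may be lost.** A reader might infer that all early progressors are dropped. The documents do not support that: the first scheduled scan comes after the 8-week gate, and Section 9 lets dosing continue until progression is confirmed and sometimes beyond. Entry also requires ECOG 0-1 and life expectancy above 6 months, which should limit early deaths.

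**Conclusion.** The gap stands: the only efficacy population selects on post-treatment outcome, and the plan does not say whether it supplies R. This should be fixed before analysis.

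A reader might go further and infer that the trial's false-positive risk is inflated. The documents do not support that. Direction depends on an excluded share and mix that they do not give. Inflation needs N to be cut or patients replaced, and also a preponderance of failures among those excluded. At a half mix, size under replacement is 0.090 or less up to 15% excluded. The figures of 0.121 and 0.211 are bounds in which every excluded patient is a failure. The move from 0.140 to 0.091 or 0.085 shows how much one removed failure can matter; it is not an expected error rate. On the reading closest to the written statistic (N=27, no replacement) the harm is lost power, not a higher false-positive risk.

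Confidence is medium: the missing definition is plain in the text, but the bias that would result is not known.

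**What to change.** In Section 12.4, define the primary PFS set as all eligible Phase II patients who received any study drug, with N1 and N2 equal to those numbers. Count death or documented progression before the landmark as failure, however long the patient was treated. Keep toxicity stops in the set and classify them from the scans already planned in Appendix H. Retain the current evaluable set as a sensitivity analysis.

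State in advance how unknown landmark status is handled. Some unknowns are likely, because Appendix H scanning ends when standard therapy or another study begins. Counting unknowns as failures is one conservative option, not the only defensible one. If status is missing for reasons unrelated to outcome, each rate is multiplied by (1−m), where m is the unknown share. Power then falls from 0.72 to 0.54 at 5% unknown and 0.37 at 10%, with size 0.037 and 0.018. Report a Kaplan-Meier landmark estimate alongside.

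In Section 4.3, state that replacement does not remove Phase II patients from the primary PFS analysis.

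The cost is wording in two sections, with no additional patients or scans. The main trade-off is the possible power loss from the rule for unknown status.

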12.5 Interim Analysis and Criteria for Early Termination of the Study

This is a Phase I/II study and as such will be monitored and discussed by RPCI's Phase 1 Committee, which meets on a regular basis per the RPCI Data Safety Monitoring Plan. Drug safety will be monitored and evaluated continuously throughout the study including 30-day safety follow-up period by obtaining, reviewing and analyzing data on AEs, changes in laboratory values, vital signs, electrocardiograms (ECGs), and physical examination findings. Potential early termination decisions are an inherent part of the Phase 1 study monitoring. The Phase II study does not have an interim analysis point.

13 CORRELATIVE DATA ANALYSIS

13.1 Translational and Correlative Biomarker Endpoints

Archival and on-treatment tumor biopsies and peripheral blood will be utilized for this assessment.

- Olaparib treatment of BRCA1/2+ve platinum resistant ovarian cancer patients leads to the release of a unique repertoire of tumor antigens that will be cross-presented to the immune system leading to generation of humoral and T cell responses. We will initially focus on auto-antibody analysis of pre- and post- treatment samples from the patients on the clinical trial, using a previously validated "seromics" approach by our group (49). The results generated by the analysis of pre- and post-treatment sera may be useful individually or as signature sets as (i) diagnostic markers, preferentially immunogenic in HR-deficient ovarian cancer, (ii) prognostic markers, associated with favorable or unfavorable clinical outcome in HR-deficient ovarian cancer, and (iii) potential targets of immune responses for the development of new immunotherapeutic reagents in HR-deficient ovarian cancer.
- Immunoscore: pre- and post-treatment biopsies.
- Analysis of T-cell responses.

- Analysis of potential resistance mechanism: sequencing studies (e.g. for HR deficiency), gene expression studies and analysis for secondary genetic and epigenetic events.

14 ETHICAL AND REGULATORY STANDARDS

14.1 Ethical Principles

This study will not be initiated until the protocol and informed consent document(s) have been reviewed and approved by a properly constituted Institutional Review Board (IRB) or Independent Ethics Committee (IEC). Each participant (or legal guardian) shall read, understand, and sign an instrument of informed consent prior to performance of any study-specific procedure. It is the responsibility of the investigator to ensure that the participant is made aware of the investigational nature of the treatment and that informed consent is given.

The Investigator is responsible for the retention of the participant log and participant records; although personal information may be reviewed by authorized persons, that information will be treated as strictly confidential and will not be made publicly available. The investigator is also responsible for obtaining participant authorization to access medical records and other applicable study specific information according to Health Insurance Portability and Accountability Act regulations (where applicable).

This study will be conducted in compliance with all applicable laws and regulations of the state and/or country and institution where the participant is treated. The clinical trial should be conducted in accordance with the ethical principles embodied in the Belmont Report: Ethical Principles and Guidelines for the Protection of Human Subjects of Research, consistent with good clinical practice and the applicable regulatory requirements and according to the guidelines in this protocol, including attached appendices.

14.2 Informed Consent

The Investigator (or IRB specified designee) is responsible for obtaining written consent from each participant or the participant's legally authorized representative in accordance with GCP guidelines using the approved informed consent form, before any study specific procedures (including screening procedures) are performed. The informed consent form acknowledges all information that must be given to the participant according to applicable GCP guidelines, including the purpose and nature of the study, the expected efficacy and possible side effects of the treatment(s), and specifying that refusal to participate will not influence further options for therapy. Any additional information that is applicable to the study must also be included. Additional national or institutionally mandated requirements for informed consent must also be adhered to. The participant should also be made aware that by signing the consent form, processing of sensitive clinical trial data and transfer to other countries for further processing is allowed.

The Investigator shall provide a copy of the signed consent form to the participant and the signed original shall be maintained in the Investigator File. A copy of the signed consent form must be filed in the participant file. At any stage, the participant may withdraw from the study and such a decision will not affect any further treatment options.

